### **11. MEASUREMENT OF EFFECT**

### 11.1 Development of symptomatic disease

In this study, the final endpoint is development of symptomatic MM that requires therapy. This is defined as one of the following criteria (CRAB and Myeloma defining events< MDE):

- Increased calcium levels (corrected serum calcium >0.25 mmol/dL above the upper limit of normal or >.275 mmol/dL) due to myeloma
- Renal insufficiency (attributable to myeloma);
- Anemia (Hb 2g/dL below the lower limit of normal or <10g/dL) due to myeloma
- Bone lesions (lytic lesions or generalized osteoporosis with compression fractures)
- Or any MYELOMA DEFINING EVENTS (MDE) as follows:
  - $\circ$  Clonal bone marrow plasma cell percentage > 60%
  - An abnormal FLC-ratio  $\geq 100$  (involved kappa) or < 0.01 (involved lambda)
  - 2 or more focal lesions on MRI or PET-CT studies

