#### 1.5 Primary Objectives

• To determine the proportion of high-risk smoldering multiple myeloma patients who are progression free (free of symptomatic Myeloma defining events) at 2 years after receiving Ixazomib and lenalidomide + dexamethasone combination therapy

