### 2.4 Definition of SMM

The diagnosis of smoldering (asymptomatic) multiple myeloma (SMM) is based on :

- Serum monoclonal protein (IgG or IgA) ≥ 3.0 g/dL or urinary monoclonal protein ≥500 mg per 24 h and/or clonal bone marrow plasma cells 10–60%.
- Absence of myeloma defining events or amyloidosis
- No evidence of the following CRAB criteria or other Myeloma defining events (MDE):
  - Increased calcium levels (corrected serum **calcium** >0.25 mmol/dL above the upper limit of normal or >.275 mmol/dL) related to MM
  - **Renal** insufficiency (attributable to MM)
  - Anemia (Hb 2g/dL below the lower limit of normal or <10g/dL) related to MM
  - **Bone** lesions (lytic lesions or generalized osteoporosis with compression fractures)

New MDE criteria that indicates overt MM and not SMM 43,44

The following criteria are now incorporated with the CRAB criteria to indicate that patients meet criteria for therapy as symptomatic or overt MM:

- Bone marrow plasma cells > 60%
- Serum involved/uninvolved FLC ratio ≥ 100, provided the absolute level of the involved free light chain is at least 100 mg/L and repeated twice\*
- MRI with two or more focal lesion that is at least 5 mm or greater in size

\*If serum free light chain ratio is stable (not increasing) for greater than or equal to six months, the patient may be eligible after discussion with the overall PI (Free Light Chain Smoldering Myeloma)

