#### **3.2 Exclusion Criteria**

- 3.2.1 No evidence of CRAB\* criteria or new criteria of active MM which including the following:
  - Increased calcium levels (corrected serum calcium > 0.25 mmol/dL above the upper limit of normal or > 0.275 mmol/dL) related to MM
  - Renal insufficiency (attributable to MM)
  - Anemia (Hb 2g/dL below the lower limit of normal or <10g/dL) related to MM
  - Bone lesions (lytic lesions or generalized osteoporosis with compression fractures)
  - Bone marrow plasma cells > 60%
  - Serum involved/uninvolved FLC ratio ≥ 100, provided the absolute level of the involved free light chain is at least 100 mg/L and repeated twice
  - MRI with two or more focal lesion that is at least 5 mm or greater in size

\*Participants with CRAB criteria that are attributable to conditions other than the disease under study may be eligible

- 3.2.2 Other concurrent chemotherapy, immunotherapy, radiotherapy, or any ancillary therapy considered investigational. Prior therapy with bisphosphonate is allowed. Prior radiation therapy to a solitary plasmacytoma is allowed.
- 3.2.3 Serious medical or psychiatric illness likely to interfere with participation in this clinical study.
- 3.2.4 Diagnosed or treated for another malignancy within 2 years of enrollment, with the exception of complete resection of basal cell carcinoma or squamous cell carcinoma of the skin, an in situ malignancy, or low-risk prostate cancer after curative therapy.
- 3.2.5 Uncontrolled intercurrent illness including, but not limited to, ongoing or active infection, symptomatic congestive heart failure, unstable angina pectoris, cardiac arrhythmia, or psychiatric illness/social situations that would limit compliance with study requirements.
- 3.2.6 Pregnant or nursing women will be excluded from the study because lenalidomide is an agent with the potential for teratogenic or abortifacient effects.
- 3.2.7 History of allergic reactions attributed to compounds of similar chemical or biologic composition to ixazomib or lenalidomide.

- 3.2.8 Known seropositive for or active viral infection with human immunodeficiency virus (HIV), hepatitis B virus (HBV) or hepatitis C virus (HCV). Patients who are seropositive because of hepatitis B virus vaccine are eligible.
- 3.2.9 Major surgery within 14 days before first dose of ixazomib.
- 3.2.10 Known Amyloid involvement.
- 3.2.11 Myeloma-related central nervous system involvement.

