| Partial Response
(PR)    | $\geq 50\%$ reduction of serum M-protein and reduction in 24-h urinary M-protein by
> 90% or to < 200mg per 24 hours. If the serum and urine M-protein are
unmeasurable, a $\geq 50\%$ decrease in the difference between involved and
uninvolved free light chain levels is required in place of the M-protein criteria
(definition of measurable disease in Section 10.2.3). If serum and urine M-
protein are unmeasurable, and serum free light assay is also unmeasurable, $\geq$
50% reduction in plasma cells is required in place of M-protein, provided
baseline bone marrow plasma cell percentage was $\geq$ 30%. In addition to the
above listed criteria, if present at baseline, a > 50% reduction in the size of soft
tissue plasmacytomas is also required.   |
|-----------------------------|--|
| Stable Disease
(SD)      | Not meeting criteria for CR, VGPR, PR or progressive disease.
This is not recommended as an indicator of response; stability of
disease is best described by providing the time to progression
estimates.   |
| Progressive
Disease (PD) | $\begin{array}{lll} > 25\% \mbox{ increase of serum M-protein (which must also be an absolute increase of $\ge$ 0.5 g/dL) and/or urine M-protein (which must also be an absolute increase of $\ge$ 200 mg/24hr). If serum and urine M-protein are unmeasurable, there must be an absolute increase of $\ge$ 10 mg/dL between involved and uninvolved FLC levels. PD is also measured by an absolute increase in bone marrow plasma cells $\ge$ 10%. In addition to the above listed criteria, progression may also be measured by a definite development of new bone lesions or soft tissue plasmacytomas or definite increase in the size of existing bone lesions or soft tissue plasmacytomas or development of hypercalcemia (corrected serum calcium $\ge$ 11.5 mg/dL or 2.65 mmol/L) that can be attributed solely to the plasma cell proliferative disorder. \end{tabular}$ |

\*Clarifications to IMWG criteria for coding CR and VGPR in patients in whom the only measurable disease is by serum FLC levels: CR in such patients indicates a normal FLC ratio of 0.26 to 1.65 in addition to CR criteria listed above. VGPR in such patients requires a > 90% decrease in the difference between involved and uninvolved FLC levels.

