| Progressive
disease (PD)
(for
participants not
in CR) | > 25% increase d in 24-hour urinary light chain excretion, which must also be an absolute increase of at least 200 mg/24 h and confirmed on a repeat investigation.       |
|   | > 25% increase d in plasma cells in a bone marrow aspirate or on trephine biopsy, which must also be an absolute increase of at least 10%.                                |
|   | Definite increase in the size of existing lytic bone lesions or soft tissue plasmacytomas.   |
|   | Development of new bone lesions or soft tissue plasmacytomas (not including compression fracture).   |
|   | Development of hypercalcemia (corrected serum calcium >11.5 mg/dL or 2.8 mmol/L not attributable to any other cause).  |
|   | Required at least one of the following:  |
|   | Reappearance of serum or urinary paraprotein on immunofixation or
routine electrophoresis confirmed by at least one follow-up and
excluding oligoclonal immune reconstitution. |
| Relapse from CR   | $\geq$ 5% plasma cells in the bone marrow aspirate or biopsy.  |
| I   | Development of new lytic bone lesions or soft tissue plasmacytomas or definite increase in the size of residual bone lesions (not including compression fracture).                   |
|   | Development of hypercalcemia (corrected serum calcium $> 11.5$ mg/dL   |
|   | or 2.8 mmol/L not attributable to any other cause) <math>e</math> .   |

a Based on the criteria reported by Blade et al., 1998.

b Per Blade *et al.*, 1998, if absence of the monoclonal protein is sustained for 6 weeks it is not necessary to repeat the bone marrow except in participants with nonsecretory myeloma where the marrow examination must be repeated after an interval of at least 6 weeks to confirm CR.

c Per Blade *et al.*, 1998, skeletal X-Rays are not required for the definition of response, but if performed there must be no evidence of progression of bone disease (no increase in size or number of lytic bone lesions).

d It is suggested that the reference point for calculating any increase should be the lowest value of the preceding confirmed response (MR, PR or CR) or the baseline value if there is no previous confirmed response.

e Other clinical data may be requested by the IRC, as necessary, to assess the cause of the hypercalcemia.

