### 13.1.1 Analysis of Primary Endpoint

Time to progression (TTP) is defined as the time from protocol therapy initiation until documented progression, censored at date last known progression-free for those who have not progressed. At time of final analysis, the 2-year progression-free rate will be estimated using the Kaplan-Meier method with 95% confidence interval. All patients who have received one dose of study treatment will be included for the TTP analysis, including those who die or are lost to follow-up within 2 years.

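### The calcium thresholds contain a unit slip in the event and eligibility rule and a wrong conversion in the PD tables, and the primary analysis does not say which rule dates the event

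*Combined protocol and SAP*

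**What the plan says.** The protocol holds three sets of calcium rules.

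- **Event and eligibility.** Section 11.1, which defines symptomatic myeloma, uses "corrected serum calcium >0.25 mmol/dL above the upper limit of normal or >.275 mmol/dL". Exclusion criterion 3.2.1 has "corrected serum calcium > 0.25 mmol/dL above the upper limit of normal or > 0.275 mmol/dL". Section 2.4 (">0.25 mmol/dL above the upper limit of normal or >.275 mmol/dL") and the Study Population part of the Protocol Summary carry the same two limbs.
- **IMWG PD.** The PD row in 11.2.3.1 sets hypercalcemia at or above "11.5 mg/dL or 2.65 mmol/L".
- **Modified EBMT PD and relapse from CR.** The table in 11.2.4.2 uses "corrected serum calcium >11.5 mg/dL or 2.8 mmol/L not attributable to any other cause" for PD and repeats the two figures for relapse from CR.

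On the primary endpoint, section 1.5 speaks of patients "progression free (free of symptomatic Myeloma defining events) at 2 years", which points to 11.1. Section 13.1.1 says: "Time to progression (TTP) is defined as the time from protocol therapy initiation until documented progression". It cross-refers neither to 11.1 nor to the PD table. Section 11.2.6 calls PFS the primary endpoint and defines it by disease progression or death.

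**The concern.** These are decision thresholds, not background. They determine who may enrol, what counts as symptomatic disease and what counts as PD. Two of them look wrong on their face. The first limb of the event rule adds to the upper limit an amount almost as large as the whole of the second limb. The IMWG row gives two figures as alternatives for one threshold, and the EBMT table pairs the same mg/dL figure with a different mmol/L figure, so both pairings cannot be right.

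At stake is whether one patient with one calcium value is classified the same way whatever unit the local laboratory reports. Calcium is in the chemistry panel. The Study Calendar (section 10) schedules that panel on day 1 of cycles 1 to 9, every 3 months in cycles 10 to 24, at end of treatment and every 3 months in event monitoring. Imaging is scheduled only at screening and end of treatment. Calcium is therefore one of the more often checked criteria, and progression also feeds PFS and duration of response.

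**Working it through.** **Inputs.** The thresholds are those quoted from 11.1, 3.2.1, 11.2.3.1 and 11.2.4.2. The molar mass of calcium is not in the documents. I assume 40.08 g/mol, so 1 mmol/L = 4.008 mg/dL; taking 40.0 to 40.1 changes nothing material. Also, 1 mmol/dL = 10 mmol/L.

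**Step 1: the plan's own IMWG pairing.** 11.5 / 4.008 = 2.87 mmol/L (2.868 to 2.875 over the molar-mass range), not 2.65. In reverse, 2.65 x 4.008 = 10.6 mg/dL. The pairing does not reproduce: the gap is 0.22 mmol/L, or 0.9 mg/dL.

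**Step 2: the EBMT pairing.** 2.8 x 4.008 = 11.2 mg/dL, against the stated 11.5. The gap is 0.07 mmol/L, or 0.3 mg/dL.

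**Step 3: the event and eligibility limbs.**

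- Limb 2: 0.275 mmol/dL = 2.75 mmol/L = 11.0 mg/dL.
- Limb 1: 0.25 mmol/dL = 2.5 mmol/L = 10.0 mg/dL above the upper limit of normal (ULN). With an assumed ULN of 2.40 to 2.65 mmol/L, it is reached at 4.90 to 5.15 mmol/L (19.6 to 20.6 mg/dL).
- As written, limb 1 would come first only if ULN + 2.5 < 2.75, that is, a ULN below 0.25 mmol/L (1.0 mg/dL). No laboratory has such a limit.
- Read per litre, limb 1 would come first if ULN + 0.25 < 2.75, that is, a ULN below 2.50 mmol/L (10.0 mg/dL). At a ULN of 2.40 the operative threshold would be 2.65 mmol/L; at 2.55 it would stay at 2.75.

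**Step 4: apply each rule to the same value.**

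| Calcium, mmol/L (mg/dL) | 11.1, limb 2 | IMWG, mmol/L figure | IMWG, mg/dL figure | EBMT, mmol/L figure | EBMT, mg/dL figure |
|---|---|---|---|---|---|
| 2.60 (10.4) | no | no | no | no | no |
| 2.70 (10.8) | no | yes | no | no | no |
| 2.78 (11.1) | yes | yes | no | no | no |
| 2.83 (11.3) | yes | yes | no | yes | no |
| 2.90 (11.6) | yes | yes | yes | yes | yes |

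All the rules agree only below 2.65 mmol/L or above about 2.87 mmol/L (10.6 and 11.5 mg/dL).

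**Step 5: the design.** With n = 53 and success declared at 33 or more progression-free patients, the exact type I error at 50% is 0.0492 and power at 70% is 0.914. These match the 0.05 and 0.91 in 13.1. Then 53 / 0.95 = 55.8, so 56. No calcium threshold enters this calculation.

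**The case against.** The strongest reply is that this is a units correction with little consequence, and much of that stands.

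- **Working threshold.** The two limbs in 11.1 are joined by an or. The absolute limb is in an unusual unit, but it equals 2.75 mmol/L and works. A reader might infer that the primary event has no usable calcium criterion, or that eligibility and the primary event conflict. Neither is so: the Protocol Summary, 2.4, 3.2.1 and 11.1 share one rule. At a ULN of 2.50 mmol/L or above, reading limb 1 per litre would reclassify nobody.
- **Event and PD differ by design.** A reader might infer that any gap between 11.1 and the PD tables is an error. The documents do not support that. Section 11.1 defines symptomatic disease, whereas the tables are for measuring response, and EBMT is a secondary measure. IMWG PD includes a rise in M-protein of more than 25% (with an absolute minimum), which is not an 11.1 event. A value of 11.2 mg/dL that meets 11.1 but not the 11.5 mg/dL figure is therefore no contradiction in itself. The errors are the mismatched pairings inside the tables and the mis-scaled limb.
- **Source unknown.** The tables are labelled as published criteria that cannot be seen here, so the documents do not show which figure of each pair was intended.
- **EBMT gap.** At 0.3 mg/dL it is much smaller than the IMWG gap and should not be given equal weight.

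The reply does not remove the unit dependence of PD, or the silence in 13.1.1 on which definition applies.

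**Conclusion.** Two calcium rules are wrong as written: the first limb in the four event and eligibility statements, by a factor of about ten, and the mg/dL to mmol/L pairing in the IMWG PD row, by 0.9 mg/dL. The EBMT pairing has a lesser mismatch in two places. From about 10.6 to 11.5 mg/dL, IMWG PD depends on the reporting unit.

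The mismatch can reach the primary analysis only through the undefined event in 13.1.1 and the PFS label in 11.2.6. If 11.1 alone dates the event, the PD mismatch is confined to response-based and PD-based secondary endpoints.

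The effect on the 2-year rate is probably small. It needs a myeloma-attributed calcium in that narrow band with no other event or PD criterion met. The documents give no frequency for this, so it cannot be quantified; each patient reclassified would move the rate by about 1.9 percentage points (1/53, ignoring censoring). A reader might infer that the trial's conclusion or sample size is in doubt; the documents do not support that. The result rests on the assumed molar mass and, for limb 1, on the assumed range of local upper limits. Which threshold is clinically right is not judged here.

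**What to change.** Reconcile the calcium thresholds in seven places: the Protocol Summary (Study Population), 2.4, 3.2.1, 11.1, the PD row of 11.2.3.1, and the PD and relapse-from-CR rows of 11.2.4.2. The sponsor should confirm each intended threshold and state it in both mg/dL and mmol/L with checked conversions (1 mmol/L = about 4.008 mg/dL). Paired values should then be equivalent, and limb 1 should be on the same scale as limb 2. The choice of threshold is the sponsor's.

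In 13.1.1, add one cross-reference naming the definition that dates the primary event (11.1 or 11.2.3.1), and make 11.2.6 consistent with it. Doing this before the final analysis avoids choosing a rule after a borderline case is known. The cost is wording in seven places, one cross-reference and that conforming edit to 11.2.6; no new data or procedures are needed.

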#### **Study Population:**

SELECT INCLUSION CRITERIA

- Age  $\geq$  18 years.
- High-risk smoldering myeloma based on the new Rajkumar et al criteria for high-risk disease.
- No evidence of CRAB criteria or new criteria of overt MM which includes the following:
  - Increased calcium levels (corrected serum calcium >0.25 mmol/dL above the upper limit of normal or >.275 mmol/dL) related to MM
  - Renal insufficiency (attributable to MM)
  - Anemia (Hb 2g/dL below the lower limit of normal or <10g/dL) related to MM
  - Bone lesions (lytic lesions or generalized osteoporosis with compression fractures)
  - No evidence of the following new criteria for active MM including the following: Bone marrow plasma cells >60%, Serum involved/uninvolved FLC

ratio  $\geq 100$  (light chain smoldering MM is allowed), and MRI with more than one focal lesion.

- ECOG Performance Status (PS) 0, 1, or 2.
- The following laboratory values obtained  $\leq 21$  days prior to registration:
  - $\circ$  ANC  $\geq 1000/\mu L$
  - $\circ$  PLT  $\geq$  75,000/ $\mu$ L
  - Total bilirubin  $\leq$  1.5 mg/dL (If total is elevated check direct and if normal patient is eligible.)
  - AST  $\leq$  3 x institutional upper limit of normal (ULN)
  - ALT  $\leq$  3 x institutional upper limit of normal (ULN)
  - Calculated creatinine clearance  $\geq$  30 mL/min

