#### **Definition of high-risk SMM:**

- Bone marrow clonal plasma cells  $\geq 10\%$  and  $\leq 60\%$  and any one or more of the following:
  - Serum M protein  $\geq 3.0$ g/dL (IgA, IgG, IgM, or IgD)
  - IgA SMM
  - Immunoparesis with reduction of two uninvolved immunoglobulin isotypes
  - Serum involved/uninvolved free light chain ratio  $\ge$ 8 (but less than 100)
    - Free Light Chain Smoldering Myeloma patients as defined in section 2.4 are not excluded
  - Progressive increase in M protein level (Evolving type of SMM)
    - Increase in serum monoclonal protein by ≥10% on two successive evaluations within a 6-month period
  - Bone marrow clonal plasma cells 50-60%
  - Abnormal plasma cell immunophenotype (≥ 95% of bone marrow plasma cells are clonal) and reduction of one or more uninvolved immunoglobulin isotypes
  - $\circ$  t (4;14) or del 17p or 1q gain
  - Increased circulating plasma cells
  - MRI with diffuse abnormalities or 1 focal lesion
  - PET-CT with one focal lesion with increased uptake without underlying osteolytic bone destruction
  - Urine monoclonal light chain excretion  $\geq$  500 mg/24 hours
- 3.1.3 ECOG Performance Status (PS) 0, 1, or 2 (Appendix A)
- 3.1.4 The following laboratory values obtained  $\leq 21$  days prior to registration and confirmed prior to the first dose of study drug:
  - ANC  $\geq 1000/\mu L$
  - $PLT \ge 75,000/\mu L$ . Platelet transfusions to help patients meet eligibility criteria are not allowed within 3 days before study enrollment.
  - Total bilirubin ≤ 1.5 mg/dL (If total is elevated check direct and if normal patient is eligible.)
  - AST  $\leq$  3 x institutional upper limit of normal (ULN)
  - ALT  $\leq$  3 x institutional upper limit of normal (ULN)

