#### 5.5 Criteria for Taking a Participant Off Protocol Therapy

Patients will be informed that they have the right to withdraw from the study at any time for any reason, without prejudice to their medical care.

In the absence of treatment delays due to adverse event(s), treatment may continue for 24 cycles or until one of the following criteria applies:

- Progression to overt Multiple Myeloma
- Intercurrent illness that prevents further administration of treatment
- Unacceptable adverse event(s)
- Participant demonstrates an inability or unwillingness to comply with the oral medication regimen and/or documentation requirements
- Participant decides to withdraw from the protocol therapy
- General or specific changes in the participant's condition render the participant unacceptable for further treatment in the judgment of the treating investigator

Participants will be removed from the protocol therapy when any of these criteria apply. The reason for removal from protocol therapy, and the date the participant was removed, must be documented in the case report form (CRF). Alternative care options will be discussed with the participant.

When a participant is removed from protocol therapy and/or is off of the study, the relevant Off-Treatment/Off-Study information will be updated in OnCore.

In the event of unusual or life-threatening complications, treating investigators must immediately notify the Overall PI,

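### Section 11.1 counts any FLC ratio of 100 or more (or below 0.01) as progression, without the floor and repeat that Sections 2.4 and 3.2.1 require, and without a rule for patients who enter at that level

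*Combined protocol and SAP*

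**What the plan says.** Section 11.1 says that "the final endpoint is development of symptomatic MM that requires therapy" and lets any one item on a list satisfy it. The FLC item gives a limit for each light chain type, at least 100 for kappa and below 0.01 for lambda ("involved kappa) or < 0.01 (involved lambda"). It sets no minimum FLC concentration, asks for no repeat and makes no reference to the baseline value. Section 1.5 equates being progression free with being free of myeloma-defining events, so this list feeds the primary endpoint. Section 13.1.1 has the time to progression "defined as the time from protocol therapy initiation until documented progression" and adds no FLC rule.

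Sections 2.4 and 3.2.1 use the same marker to separate overt from smoldering disease. There a ratio of 100 or more counts only "provided the absolute level of the involved free light chain is at least 100 mg/L and repeated twice".

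Some patients may enter at or above that ratio:

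- The footnote to 2.4, which makes each case a matter to raise with the lead investigator, says: "If serum free light chain ratio is stable (not increasing) for greater than or equal to six months, the patient may be eligible".
- Section 3.1.2 adds: "Free Light Chain Smoldering Myeloma patients as defined in section 2.4 are not excluded".
- The Protocol Summary notes beside its own FLC bar that "light chain smoldering MM is allowed".

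Section 5.5 lists "Progression to overt Multiple Myeloma" as a reason to stop protocol therapy. Section 5.6 ends follow-up at progression to active symptomatic disease.

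**The concern.** The protocol applies two standards to one laboratory marker. A result that does not make a patient overt at screening under 2.4 and 3.2.1 makes the same patient a progressor under 11.1.

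Two situations follow. First, a single ratio during treatment, not repeated and with a low involved FLC, is an endpoint event; under 5.5 and 5.6 it also stops treatment and ends follow-up, so it would be hard to re-score later. Second, a patient enrolled at 100 or more meets the 11.1 item from the start. Sites would probably ignore an unchanged entry ratio, but no section says so, and none says how large a change would count. In an open-label single-arm trial, with no central review of response planned (11.2.7), a primary-endpoint event should not depend on case-by-case judgement.

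**Working it through.** **1. The FLC criterion, place by place**

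| Place | Use | Floor of 100 mg/L | Repeat | Provision for a stable ratio at entry |
|---|---|---|---|---|
| Protocol Summary | Entry bar | No | No | Yes, light-chain SMM allowed |
| Section 1 (introductory text) | Background | No | No | No |
| 2.4 | Definition of overt MM | Yes | Yes | Yes, footnote |
| 3.1.2 | Eligibility | Refers to 2.4 | Refers to 2.4 | Yes, refers to 2.4 |
| 3.2.1 | Exclusion | Yes | Yes | No |
| 11.1 | Endpoint event | No | No | No |

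**2. Does another section repair 11.1?** The confirmation statements in 11.1 (under measurement of response), 11.2.3 and 11.2.3.1 concern response assessments. Stretched to cover the event list, they would still supply no floor, and a stable ratio of 100 or more would pass confirmation. Section 13.1.1 adds nothing on FLC.

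**3. Routes to a ratio of 100 or more at entry**

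- Light-chain SMM with a ratio stable for at least six months, case by case (2.4, 3.1.2, Summary). Section 3.2.1 states no such exception, so the sections are in tension, but the route is not closed.
- Involved FLC below 100 mg/L, which 3.2.1 does not exclude. The uninvolved FLC must then be below 100/100 = 1 mg/L. The documents give no frequency, and the Summary's bar, which has no floor, would exclude such a patient if read alone.

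**4. The plan's design, then an illustration.** Inputs from 13.1: 53 eligible patients, null rate 50%, alternative 70%, stated type I error 0.05 and power 0.91. No cutoff is printed. With X binomial(53, p):

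| Success if X is at least | Type I error, p = 0.5 | Power, p = 0.7 |
|---|---|---|
| 32 | 0.0845 | 0.9505 |
| 33 | 0.0492 | 0.9138 |
| 34 | 0.0267 | 0.8592 |

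Only 33 fits, so the stated design reproduces. Now let k of the 53 be counted as events whatever their course. Success then needs 33 among the other 53 − k, with probability P(X ≥ 33) for X binomial(53 − k, p):

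| k (assumed) | Power, p = 0.7 | Type I error, p = 0.5 | Drop in expected rate, 0.7k/53 |
|---|---|---|---|
| 0 | 0.914 | 0.049 | 0 |
| 1 | 0.880 | 0.035 | 1.3 points |
| 2 | 0.836 | 0.024 | 2.6 points |
| 3 | 0.782 | 0.016 | 4.0 points |

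The documents give no value for k. The planned analysis is a Kaplan-Meier estimate in all treated patients, so the binomial rule on 53 only approximates it.

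**5. Direction.** The events under the literal 11.1 item include every event under a version with floor and repeat, plus possible extras. The literal rule can therefore only lower the observed 2-year rate.

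**6. Timing, once a repeat is required.** Treatment ends at 24 × 28 = day 672, and two years is day 730. A first qualifying value at day 672, repeated only at the next scheduled visit, would be confirmed at about 672 + 91 = day 763, or about 672 + 183 = day 855 under the six-monthly option in the study calendar. Dating the event at confirmation would move it past two years. The present text, which asks for no repeat, does not have this problem.

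**The case against.** The strongest reply is that 11.1 is shorthand. The short form of the FLC criterion also stands in the Protocol Summary and the introductory text of Section 1, and 11.1 likewise drops the 5 mm lesion size given in 2.4 and 3.2.1. On this view the full definition in 2.4 governs throughout. In addition, 11.1 speaks of symptomatic disease developing, and a patient admitted because the ratio was stable has developed nothing.

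Part of this stands. The word development does suggest that an unchanged entry ratio was not meant to count, and the shorthand reading is plausible. But 11.1 goes on to define the event by its list and does not refer back to 2.4. The other short forms are a summary and background, so they do not settle how the endpoint is scored.

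A reader might infer something stronger: that every patient enrolled at 100 or more is a failure from day 1, and that the trial loses the power shown in the table. The documents do not support that. The reading is unworkable, since it would remove such patients from therapy and follow-up on entry, and the number of such patients is unknown. Nor can the omission be read as favouring the regimen, because literal application works against it.

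**Conclusion.** The inconsistency is plain in the text and sits in the definition of the primary-endpoint event. Applied as written, 11.1 counts ratios that the protocol elsewhere does not regard as overt myeloma, and it leaves patients who enter at 100 or more without a scoring rule.

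The effect is conservative: a lower observed 2-year rate and lower power, with no route to a false efficacy claim. Its size cannot be derived. The number affected may be zero; the power figures hold only for an assumed k of 1 to 3, a cutoff of 33 of 53, and all k patients counted as events. No size is put on the missing floor and repeat during treatment. If every site ignores an unchanged entry ratio, the baseline part causes no bias, but that practice is unwritten. Severity is minor to should-fix.

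**What to change.** Amend the FLC item in 11.1 as follows:

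- **Event:** ratio of at least 100 (kappa) or below 0.01 (lambda), with involved FLC of at least 100 mg/L, confirmed on a prompt repeat sample, for example an unscheduled draw within about four weeks. Say whether one repeat or two is required, since the wording in 2.4 leaves this open.
- **Date:** the first qualifying sample.
- **Baseline:** a ratio already at 100 or more (or below 0.01 for lambda) at the last pre-dose value, and not increased, is not an event. That value is Cycle 1 Day 1, or screening where the calendar's 7-day allowance is used.
- **Patients enrolled at that level:** a confirmed rise from the entry value counts. One available threshold is in 11.2.3.1, an absolute increase of at least 10 mg/dL in the difference between involved and uninvolved FLC. It is written there for patients whose serum and urine M-protein are unmeasurable, so any wider use should be stated. Alternatively, report the 2-year rate with and without such rises as events.

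Do not simply drop FLC events for patients enrolled at 100 or more. They would then stay progression free however far FLC rose, until another criterion was met, which would favour the regimen in a comparison with a fixed 50%. The maintenance footnote in 5.1 does not fill that gap: it covers only optional dexamethasone in cycles 10 to 24.

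The cost is a one-paragraph amendment and one repeat FLC sample per suspected event (more if two repeats are chosen). FLC testing is already on the study calendar.
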